7.1 Study population

Adult patients ≥18 years will be recruited at the bone marrow transplant center of the Medical University of Vienna. Patients will be eligible if 12 months +/- 1 month had passed since the allogeneic HSCT and if the patient is willing to sign an informed consent. Basic demographic data including age, gender, conditioning regimen, type of the hematopoietic graft (sister/brother, unrelated donor, cord blood) or bone marrow transplant, intensity of immunosuppressive therapy, medical history including time of previous TBE vaccination before HSCT and present status of chronic GVHD according to the NIH criteria [10] will be obtained. If available (only possible for sister/brother donor) the current TBE vaccination status of the donors will be requested. As control group, non-immunocompromised adult volunteers ≥18 years (age-matched with a tolerance of +/-10 years and sex-matched to the study population) without previous TBE-vaccination will be recruited at the outpatient clinic of the department of infectious diseases and tropical medicine of the Medical University of Vienna.

7.1.1 Subject population

Study entry is defined as the date of signature of the study participant (subject) on the informed consent form. All subjects enrolled will be assigned a subject code, which consists of a consecutive subject number (2 digits).

7.1.2 Inclusion criteria

Male and female subjects will be eligible for participation in this study if they:

- Are ≥18 years on the day of screening
- Had undergone an allogeneic HSCT 11 to 13 months ago (study population)
- Are clinical healthy without previous TBE vaccination (control group)
- Have an understanding of the study, agree to its provisions, and give written informed consent prior to study entry
- If female and capable of bearing children have a negative urine pregnancy test result at study entry and agree to employ adequate birth control measures for the duration of the study

7.1.3 Exclusion criteria

Subjects will be excluded from participation in this study if they:

• Have received a TBE vaccination following HSCT

- Suffer from extremely severe acute GVHD and therefore receive prednisone >0.5 mg/kg bodyweight as part of a combination therapy or a three agent immunosuppressive treatment (because in these HSCT patients any type of vaccination has to be postponed until immunosuppression is reduced to a double combination or prednisone <0.5 mg/kg bodyweight)
- Suffer from or have a history of previous TBE virus infection or vaccination, previous dengue virus infection or vaccination against yellow fever or Japanese encephalitis
- Have any acute febrile illness in the 2 weeks prior to or at the time of enrolment
- Have a history of severe allergic reactions or anaphylaxis after vaccination
- If female, are pregnant or lactating.
- If belonging to the healthy control group, are immunosuppressed (suffer from or have a history of immune mediated diseases, long-term use of corticosteroids, hemodialysis, chronic renal insufficiency, liver cirrhosis Child-Pugh class C, hematooncological malignant disease, solid organ transplant, HSCT)
- Suffer a relapse of their underlying malignant disease

7.1.4 Study duration

The total study duration is estimated to be four years. For the individual study participant the study duration will be 44-56 weeks.

7.1.5 Withdrawal and replacement of subjects

Criteria for withdrawal

Subjects may prematurely discontinue from the study at any time. Premature discontinuation from the study is to be understood when the subject did not undergo complete the last visit (study visit 8) and / or all pivotal assessments during the study.

Subjects must be withdrawn under the following circumstances:

- at their own request
- if the investigator feels it would not be in the best interest of the subject to continue
- if the subject violates conditions laid out in the consent form / information sheet or disregards instructions by the study personal

In all cases, the reason why subjects are withdrawn must be recorded in detail in the CRF and in the subject's medical records. Should the study be discontinued prematurely, all study materials (complete, partially completed and empty CRFs) will be retained.

Follow-up of patients withdrawn from the study

In case of premature discontinuation after start of vaccination, no further investigations concerning the study will be performed. Furthermore, participants may request that from the time point of withdrawal no more data will be recorded and that all biological samples collected in the course of the study will be destroyed.

Replacement policy

If the week 8 (primary endpoint) is reached, drop-outs will be included in the sample size. If the participiant drops out before the week 8 is reached, patients will be replaced and the next free subject number will be allocated.

7.1.6 **Premature termination of the study**

The sponsor has the right to close this study at any time. The IEC and the competent regulatory authority must be informed within 15 days of early termination.

The trial or single dose steps will be terminated prematurely in the following cases:

- If adverse events occur which are so serious that the risk-benefit ratio is not acceptable.
- If the number of dropouts is so high that proper completion of the trial cannot realistically be expected.

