10. FOLLOW-UP

No follow-up of the patient is required for this study.

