11.1 Sample size considerations

For our phase II pilot study a calculation of the sample size was performed using nQuery 6.1. The primary endpoint is the outcome of the NT against 4 weeks after the second vaccination (positive test: Yes/No). Because of deviation of the antibody concentrations from normal distribution (NT level <=10 not detectable indicating a negative test), the outcome is reduced to a binary but clinically more relevant outcome (seroconversion rate: NT levels >10 indicates a positive test). Previously, in a study with heart transplant recipients a seroconversion rate of 35% was detected compared to 100% in the healthy control group [21]. In our study we expect a seroconversion nate of at least 90% in the healthy control group. In the HSCT patients we expect a seroconversion not exceeding 50%. The calculation of the sample size was performed using the following assumption: Significance level alpha 0.05, Power 0.8, ratio of HSCT patients/healthy volunteers: 1/1. With a total number of 46 participants (23 HSCT patients and 23 healthy volunteers) the assumed difference in the seroconversion rate between groups can be detected (using a two-sided Fisher's Exact Test) with 80% Power. We added 10% to adjust for potential loss-to-follow-up which results in 26 HSCT patients and 26 healthy volunteers.

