11.2 Relevant protocol deviations

All protocol deviations will be listed in the study report. Major deviations regarding to subjects safety will lead to withdrawal.

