11.4 Missing, unused and spurious data

Only subjects for whom data are available will be included in the statistical analysis. Missing values will neither be replaced nor estimated.

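### Study withdrawal ends all investigations even in consenting subjects, so a two-dose subject withdrawn before Visit 4 gives no primary outcome, and the HSCT seroconversion rate may be overstated

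*Combined protocol and SAP*

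**What the plan says.** Section 7.1.5 lists three grounds for mandatory withdrawal: the subject's own request, the investigator's view of the subject's interest, and failure to keep to the consent conditions or to staff instructions. Section 11.2 adds another: "Major deviations regarding to subjects safety will lead to withdrawal". One consequence follows for all of them: "In case of premature discontinuation after start of vaccination, no further investigations concerning the study will be performed". The next sentence in 7.1.5 gives subjects a further, separate right to stop data recording and have their samples destroyed, so the end of investigations does not depend on withdrawn consent.

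On replacement, 7.1.5 says: "If the week 8 (primary endpoint) is reached, drop-outs will be included in the sample size". Subjects who leave before that point are replaced.

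Section 8.1.3 deals separately with interrupting or discontinuing the vaccine. It requires the reason to be documented and is silent on later visits.

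The primary analysis (11.3) takes eligible subjects with an antibody result. Section 11.4 adds: "Only subjects for whom data are available will be included in the statistical analysis". Missing values are not imputed, and no sensitivity analysis is planned.

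**The concern.** The primary endpoint is the neutralization test result four weeks after the second dose, drawn at Visit 4. A subject who has had both doses and is then withdrawn has a response that can be measured, and may be willing to have it measured, but the protocol forbids the draw. Replacement restores the head count but not the missing outcome.

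The two groups are unlikely to lose subjects for the same reasons. Relapse, GVHD and intensified immunosuppression arise only in the HSCT group, and section 5.1 says that immunosuppressive regimens may weaken the response to vaccination. If the HSCT patients lost are the poorer responders, the reported HSCT rate is too high and the deficit that the trial looks for appears smaller.

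Safety data have a smaller gap. After the 30-minute observation, adverse events are collected by asking at the next visit (8.5.2). The synopsis makes systemic reactions the tolerability endpoint, and 9.1.1 says these usually appear within 72 hours. A subject withdrawn between a dose and the next visit has no scheduled enquiry that would capture them.

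**Working it through.** **Inputs from section 11.1.** The planning assumptions are "Significance level alpha 0.05, Power 0.8, ratio of HSCT patients/healthy volunteers: 1/1". The control rate is assumed to be "of at least 90% in the healthy control group" (0.90 used here), and the HSCT rate is at most 50% (0.50 used). The plan gives 23 evaluable per group, "using a two-sided Fisher's Exact Test) with 80% Power", raised to 26 for 10% loss.

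**Step 1: reproduce the plan's figure.** Exact power is the sum of the two binomial probabilities over all tables that the two-sided Fisher test rejects at 0.05.
- 22 per group: 78.6%
- 23 per group: 81.1%
- 26 per group: 85.5%

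The stated 23 is confirmed. The allowance is also right: 23/0.9 = 25.6 and 23 × 1.1 = 25.3, and both round up to 26.

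**Step 2: follow a two-dose subject withdrawn before Visit 4.** Section 7.1.5 stops the draw, and replacement fills the place. Sections 11.3 and 11.4 exclude the subject. Both the 10% allowance and replacement protect the number of subjects, but neither protects the rate.

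**Step 3: size of the bias.** Let p be the true HSCT rate, d the share of HSCT subjects lost before Visit 4, and q the response rate among those lost. Then the observed rate = (p − d·q)/(1 − d). The values of d and q are assumptions, as neither is in the documents. Loss is taken to occur in the HSCT group only, with controls at 90%.

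| d | q | Observed HSCT rate | Power, 26 per group | Power, 23 per group |
|---|---|---|---|---|
| any | 50% (non-selective) | 50% | 85.5% | 81.1% |
| 10% | 25% | (0.50 − 0.025)/0.90 = 52.8% | 80.0% | 75.5% |
| 10% | 0% | 0.50/0.90 = 55.6% | 73.6% | 69.1% |
| 20% | 25% | (0.50 − 0.05)/0.80 = 56.25% | 71.8% | 67.4% |
| 20% | 0% | 0.50/0.80 = 62.5% | 54.3% | 50.4% |

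The 26-per-group column is the relevant one, because losses before week 8 are replaced. In counts, 13 of 26 responders is 50%. If three non-responders are lost, the result is 13 of 23, or 56.5%.

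**Step 4: the replacement wording.** Visit 2 falls on day 26 to 30, and Visit 4 follows it by 21 to 35 days. The serum may therefore be drawn from day 26 + 21 = 47 to day 30 + 35 = 65, up to nine days either side of day 56. Within that window, reaching week 8 and having the sample are different events.

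**The case against.** The strongest reply is that the quoted rule concerns leaving the study, not stopping the vaccine. This is correct. A reader might infer that anyone who stops vaccination loses all further visits, but 8.1.3 handles vaccine discontinuation separately and does not say so. It leaves the matter open. No dose is scheduled between Visits 2 and 4, so stopping the vaccine after dose 2 affects only the third dose. After one dose the primary endpoint is not defined at all. The firm case is therefore the two-dose subject withdrawn from the study before Visit 4.

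A reader might also infer that replacement is triggered purely by a date and so loses outcomes selectively. The text does not support this, because the parenthesis in "If the week 8 (primary endpoint) is reached, drop-outs will be included in the sample size" allows week 8 to mean the assessment. Even on the date reading, a subject sampled on day 47 who leaves on day 50 is still analysed under 11.3, and the only effect is one extra recruit. A subject who leaves on day 58 unsampled is the kind of loss that the 10% allowance covers. What remains is an ambiguity in the wording.

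It would also be wrong to say that safety follow-up ends altogether. Serious adverse event outcomes (9.5.1), pregnancies (9.2.4) and withdrawal reasons (7.1.5) are still captured, and CRFs are completed for non-completers (12.1.1). Section 10 says "No follow-up of the patient is required for this study", but this is a general statement that does not mention withdrawn subjects and adds little.

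Finally, selective loss is an inference. If those lost respond like the rest, there is no bias.

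**Conclusion.** The point holds for subjects withdrawn from the study after vaccination has started. The protocol forbids collecting a primary outcome that a consenting two-dose subject could still give, and the analysis then leaves that subject out. Non-serious adverse events after withdrawal are not actively sought.

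With 10% of HSCT patients lost and 0% to 25% of them responding, the HSCT rate is overstated by 2.8 to 5.6 percentage points. Power falls from 85.5% to between 80.0% and 73.6%. These figures rest on a true rate of 50%, controls at 90%, loss in the HSCT group only, 26 evaluable per group, and assumed values for the share lost and its response rate. The 20% rows and the 23-per-group column in the table mark less favourable assumptions and are not predictions. The documents do not show that loss will be selective, only that the plan could neither prevent nor detect it. The sample size itself needs no change.

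**What to change.** 1. In 7.1.5 and 8.1.3, separate three events: stopping vaccination, withdrawal from the study by the investigator, and withdrawal of consent. State for each which visits continue. This concerns data collection only and leaves the grounds for stopping vaccination as they are.
2. For subjects who still consent, keep the scheduled Visit 4 serum draw and the adverse event enquiry.
3. In 11.3, include the results of subjects who had both doses in the primary analysis. Report one-dose subjects, sampled at nominal day 56, only in a sensitivity analysis, for example counted as non-responders. The endpoint is defined after the second dose, so adding them to the primary analysis would change the question.
4. As a clarification, make replacement depend on whether the Visit 4 serum sample has been obtained, in place of week 8 being reached.

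The cost is protocol wording, a little follow-up effort, and one already planned 10 ml draw in a few subjects.

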8. METHODOLOGY

8.1 Study medication

Active agent and characteristics: Inactived TBE-virus adsorbat vaccine. One dose (0.5 ml) contains 2.4 µg of formaldehyde inactivated TBE-virus (strain Neudörfl) and 1 mg aluminium hydroxide as adjuvant.

Trade name of the agent: FSME IMMUN 0.5 ml Manufacturer: PFIZER Drug supply: PFIZER

Storage Instructions: The vaccine has to be stored in a refrigerator at 2-8°C in the orginal package.

Route of administration: intramuscular injection.

8.1.1 Dosage and administration

Initial dose: All subjects will receive one dose 0.5 ml TBE vaccine FSME IMMUN on day 0 (study visit 1).

Repeated dose: All subjects will receive one additional dose 0.5 ml TBE vaccine FSME

IMMUN on week 4 (study visit 2) and between week 40-52 (study visit 6).

Route of administration: TBE vaccine will be injected intramuscularly in the Musculus deltoideus.

Duration: All subjects will receive 0.5 ml TBE vaccine three times within one year.

8.1.2 Study-drug up- and down titration

Not needed for the study.

8.1.3 Study drug interruption or discontinuation

The investigator must temporarily interrupt or permanently discontinue the study drug if continued administration of the study drug is believed to be contrary to the best interests of the patient.

The interruption or premature discontinuation of study drug might be triggered by an AE, a diagnostic or therapeutic procedure, an abnormal assessment, or for administrative reasons, in particular withdrawal of the patient's consent.

The reason for study drug interruption or premature permanent discontinuation must be documented in the CRF.

8.1.4 Study-drug delivery & drug storage conditions

The drug will be ordered from the local pharmacy of the General Hospital of Vienna. After receipt the vaccine will be stored in the refrigerator at 2-8°C in the original package at the outpatient clinic of the Department of Internal Medicine I, Division of Infectious Diseases and Tropcial Medicine. The vaccine should not be frozen or stored at a temperature >8°C.

8.1.5 Study drug packaging and labeling

Packaging and labeling of the TBE vaccine is done by the producer according to local legal requirements and GMP and shipped to the local pharmacy of the General Hospital of Vienna.

8.1.6 IMP administration & handling

Before application the vaccine has to reach room temperature. Furthermore, the suspension has to be thrilled and has to be injected intramuscularly in the musculus deltoideus immediately after the protecting cap is removed from the needle. Longer, unprotected resting can lead to unsterility and/or occlusion of the needle. All vaccines have to be documented with self-adhesive label in the vaccination card.

8.1.7 Drug Accountability

The application of the drug will be documented in the clinical records of the patient by using a self-adhesive label of the vaccine and in the CRF.

8.1.8 **Procedures to assess subjects compliance**

Due to intramuscular injection by the doctor, the compliance of the patients has not to be additionally checked.

8.1.9 Concomitant medication

Concomitant medication has to be documented in the CRF.

8.2 Randomization

Not needed for the study.

8.3 Blinding

Not needed for the study.

8.4 Benefit and risk assessment

After vaccination with the inactivated TBE virus K23, in particular following the administration of the complete primary immunization, it is highly probable that the majority of subjects participating in the phase II clinical study will be protected against TBE, one of the most severe infections of the central nervous system. Allogeneic HSCT recipients, particularly those with chronic GVHD, have a high risk for microbial infections including TBE infection. Therefore, primary vaccination of HSCT recipients is recommended in risk areas one year

after HSCT at the latest independently of previous TBE vaccination before HSCT. The used TBE-vaccine is registered in Austria for more than one decade. Its safety and efficacy have been already demonstrated in many clinical trials. Therefore, unexpected adverse events due to the vaccination are not assumed. However, the following side effects have to be considered:

- very common (>1/10): local reactions at the site of injection, transient redness, and swelling.

- common (>1/100;<1/10): systemic reactions including fever, fatigue, headache, muscular pain, arthralgia. These side-effects usually occur within 72 hours after the vaccination, abate within 1-2 days, but do not acquire any medical treatment. All adverse events will be listed in the study documents and have to evaluated by the investigator for causality to the vaccination. After venous puncture local reactions, a hematoma or phlebitis can occur. However, the planed venous punctures withdraw only minor volumes of blood and do not impair the patient's health.

Therefore, it can be speculated that this study does not exhibit an exceptional risk for the patients.

8.5 Study procedures

8.5.1 General rules for trial procedures

- All study measures like blood sampling and measurements have to be documented with date (dd:mm:yyyy).
- In case several study procedures are scheduled at the same time point, there is no specific sequence that should be followed.
- The dates of all procedures should be according to the protocol. The time margins mentioned in the study flow chart are admissible. If for any reason, a study procedure is not performed within scheduled margins a protocol deviation should be noted, and the procedure should be performed as soon as possible or as adequate.
- If it is necessary for organizational reasons, it is admissible to perform procedures which are scheduled for one visit at two different time points. Allowed time margins should thereby not be exceeded.

8.5.2 Study visits

8.5.2.1 Visit 0/ Screening investigation (Day -28)

The investigator will inform the subject about the procedures, risks and benefits oft he study. Fully informed, written consent must be obtained from each subject prior to any assessment being performed. It is important that the subject is allowed sufficient time to consider his/her participation in the study.

The following assessments will be performed:

- Inclusion and exclusion criteria.
- Demographic data including sex, age, weight and height.
- Medical history and information on planned hospitalization (including elective surgery) during the study for medical conditions existing prior to study entry.
- Physical examination including body temperature measured axillary.
- Pregnancy test in females capable of bearing children.
- Blood draw of 10 ml blood for TBE antibody level detection.
- Blood draw of 40 ml blood for cellular immunity.
- Blood draw of 10 ml blood for immune status and quantitative immunoglobulin levels in HSCT patients only.

Subjects who suffer from an acute illness with or without elevated body temperature (\geq 37.5°C, measured axillary with two weeks prior to screening will not be vaccinated. In this case Visit 1 will take place separately at a later date, as long as the study is ongoing.

8.5.2.2. Visit 1 /First Vaccination (Day 0)

The following activities will be performed before vaccination only when Visit 0 and Visit 1 are not the same day

- Review of inclusion and exclusion criteria
- Medical history update
- Physical examination including body temperature measured axillary
- Pregnancy test in females capable of bearing children.

Then the subject will receive the first vaccination. For vaccination the following procedures have to be considered:

- The vaccine has to reach room temperature before administration of the vaccine
- The vaccine has to be shaken vigorously for five to ten seconds
- The injection site has to prepared according to standard clinical procedures
- After removement of the protecting cap from the needle the 0.5 ml dose of the vaccine has to be administered immediately by intramuscular injection into the musculus deltoideus in the upper arm.

Following vaccination, the subject will be oserved for at least 30 minutes. Any infection site reactions and systemic adverse experiences will be recorded.

